6.15.3 Amyotrophic Lateral Sclerosis Assessment Questionnaire, 40 questions (ALSAQ-40)

ALSAQ-40 will be measured at Day 240 and Day 365. Values of each question, subscales (Physical Mobility, Activities of Daily Living/Independence, Eating and Drinking, Communication and Emotional Functioning) with imputed values as described in section 6.2.10 and their changes from baseline will be presented with descriptive statistics for each visit by treatment group (Tables 14.3.6.4.1-14.3.6.4, Listing 16.2.9.4).

6.15.4 Clinical Global Impression of Change (CGIC) and Patient Global Impression of Change (PGIC)

QMD Ref: Worldwide-TMP-ST-005-7.0 Effective: 12Aug2019	Governing QMD: Worldwide-SOP-ST-001
Confidentiality Statement	

This document is the property of Worldwide Clinical Trials Inc. and may not be duplicated, copied, altered or removed from company without prior approval from Worldwide Quality Assurance or in compliance with Worldwide Standard Operating Procedures.

Worldwide Clinical Trials Controlled Quality Management Document			
 WORLDWIDE CLINICAL TRIALS	Sponsor:	Helixmith Co., Ltd.	
	Protocol Number:	VMALS-002-2b	
STATISTICAL ANALYSIS PLAN. PHASE 2-3-4			

CGIC and PGIC will be measured at Day 240 and Day 365. Global improvement, Efficacy index, Impression of change and Degree of Change will be presented with descriptive statistics for each visit by treatment group (Tables 14.6.5 and 14.6.6, Listings 16.2.9.5 and 16.2.9.6).

6.15.5 Slow vital capacity (SVC)

SVC will be measured at Day 240, Day 300 and Day 365. % predicted, best vital capacity, second best vital capacity and third best vital capacity and their changes from baseline will be presented with descriptive statistics by visits and treatment group (Table 14.6.7, Listing 16.2.9.7).

6.15.6 Time to tracheostomy

Time to tracheostomy will be presented with descriptive statistics and corresponding survival curves using Kaplan- Meier analysis (Table 14.6.8, Listing 16.2.9.8).

SAS code example for Kaplan-Meier analysis:

```
proc lifetest data=DATAIN method = km;
  time AVAL*CNSR(1);
  strata TRT01PN / test = logrank;
run;
```

DATAIN – source dataset

AVAL – time to event

CNSR – flag for censoring, if CNSR=1 then the corresponding value of AVAL is a censored value and not an observed event

TRT01PN – treatment group

Analysis will be performed on data combined for core study the Study VMALS-002-2 (Screening, Day 0 pre-dose, Day 30, Day 60 pre-dose, Day 84, Day 120 pre-dose, Day 144 and Day 180) and for this extension study the Study VMALS-002-2b (Day 240, Day 300, Day 365/ET4).

QMD Ref: Worldwide-TMP-ST-005-7.0 Effective: 12Aug2019	Governing QMD: Worldwide-SOP-ST-001
Confidentiality Statement	

This document is the property of Worldwide Clinical Trials Inc. and may not be duplicated, copied, altered or removed from company without prior approval from Worldwide Quality Assurance or in compliance with Worldwide Standard Operating Procedures.

Worldwide Clinical Trials Controlled Quality Management Document			
 WORLDWIDE CLINICAL TRIALS	Sponsor:	Helixmith Co., Ltd.	
	Protocol Number:	VMALS-002-2b	
STATISTICAL ANALYSIS PLAN. PHASE 2-3-4			

6.15.7 Time to all-cause mortality

Time to all-cause mortality will be presented with descriptive statistics and corresponding survival curves using Kaplan-Meier analysis (Table 14.6.9, Listing 16.2.9.8). Analysis will be performed on data combined for core study the Study VMALS-002-2 and for this extension study the Study VMALS-002-2b.

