5. STUDY POPULATION

Participants who complete the Day 180 Visit in VMALS-002-2 are eligible to enroll in this extension study, VMALS-002-2b.

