5.1. Number of Participants

The number of Participants to be enrolled in this extension study depends upon the number of Participants who complete the Day 180 Visit in VMALS-002-2 and provide written informed consent for this extension protocol (prior to, during, or after their Day 180 Visit in the VMALS-002-2 study).

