9.2. Population for Analysis: Safety Population

The safety analysis population will contain all Participants who enroll in VMALS-002-2b.

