10.3.2. Definitions

Active Infection	Chronic infection or severe active infection that may compromise the Participant's wellbeing or participation in the study, in the Investigator's judgment
Day 240, etc.	Day 240 (for example) refers specifically to the actual day of the Visit designated as the Day 240 Visit, and not to the 240 th day of the study for a Participant.
End of Study	Completion of the last Visit (Day 365) or procedures shown in the SoA for the last Participant remaining in the study
Highly Effective Contraception Method	See Contraceptive Guidance
Investigator	The PI or appropriate study site personnel whom the PI designates to perform a certain duty
Safety Analysis Population	All Participants in the study
Sponsor	Helixmith Co., Ltd. and its representatives contracted to provide services for study conduct
Participant	Anyone who is consented for the Safety Evaluation during VMALS-002-2b on or prior to Day 180 of VMALS-002-2
VM202	The active pharmaceutical ingredient of Engensis: a novel genomic complementary deoxyribonucleic acid (cDNA) hybrid human hepatocyte growth factor (HGF) coding sequence (HGF-X7) expressing two isoforms of HGF, HGF ₇₂₈ and HGF ₇₂₃

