3.2 Exploratory Endpoints

- Change from Baseline (Study VMALS-002-2 Day 0) in total mean Revised Amyotrophic Lateral Sclerosis Function Rating (ALSFRS-R) scores at Day 365 for Engensis compared to Placebo
- Change from Baseline (Study VMALS-002-2 Day 0) in ALSFRS-R subscores for Fine and Gross Motor Functions (sum of scores for items 4 to 9) and for Bulbar Function (sum of scores for items 1 to 3) at Day 365 for Engensis compared to Placebo
- Changes in the slope of the total ALSFRS-R score over time for Engensis compared to Placebo
- Change from Baseline (Study VMALS-002-2 Day 0) in muscle strength assessed bilaterally by Handheld Dynamometry (HHD) in muscles in the upper and lower extremities at Day 365 for Engensis compared to Placebo
- Change from Baseline (Study VMALS-002-2 Day 0) in Quality of Life (QoL) using the ALS Assessment Questionnaire (ALSAQ; with 40 items, ALSAQ 40) on Day 365 for Engensis compared to Placebo
- Patient Global Impression of Change (PGIC) and Clinical Global Impression of Change (CGIC) at Day 365 for Engensis compared to Placebo
- Change from Baseline (Study VMALS-002-2 Day 0) in Slow Vital Capacity (SVC) at Day 365 for Engensis compared to Placebo
- Time to tracheostomy for Engensis
- Time to all-cause mortality compared to Placebo

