6.1 Analysis Sets

6.1.1 Safety Analysis Population

The safety analysis population will contain all Participants who sign the Informed Consent of the VMALS-002-2b study. Participants will be grouped according to their actual treatment received in VMALS-002-2 study.

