6.2.3 Duration / Study Day / Time

Study day will be calculated as the number of days from first Study Injection in the Study VMALS-002-2:

- date of event – date of first Study Injection + 1, for events on or after first Study Injection in the Study VMALS-002-2
- date of event – date of first Study Injection, for events before first Study Injection in the Study VMALS-002-2

Duration of ALS diagnosis will be presented in months and calculated as (Date of Screening of the Study VMALS-002-2 – Date of Onset of Symptoms +1) / 30.4375.

QMD Ref: Worldwide-TMP-ST-005-7.0 Effective: 12Aug2019	Governing QMD: Worldwide-SOP-ST-001
Confidentiality Statement	

This document is the property of Worldwide Clinical Trials Inc. and may not be duplicated, copied, altered or removed from company without prior approval from Worldwide Quality Assurance or in compliance with Worldwide Standard Operating Procedures.

Worldwide Clinical Trials Controlled Quality Management Document			
 WORLDWIDE CLINICAL TRIALS	Sponsor:	Helixmith Co., Ltd.	
	Protocol Number:	VMALS-002-2b	
STATISTICAL ANALYSIS PLAN. PHASE 2-3-4			

Time to tracheostomy will be calculated as time from date of first Study Injection in the VMALS-002-2 Study to date of first occurrence of ALSFRS-R questionnaire with answer “**0 - Invasive mechanical ventilation by intubation or tracheostomy**” to question “**12. Respiratory insufficiency**” (ASLFRS-R date – date of the first injection +1) presented in days.

Time to all-cause mortality will be calculated as the time period from date of first Study Drug Injection in the Study VMALS-002-2 to date of death within 365 days presented in days (death date – date of the first injection +1).

Both time-to-event endpoints will be censored by date of last visit.

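### The survival analyses do not say whose data are combined; on the extension set, mortality is timed from first injection although entry requires reaching Day 180, and 'time to tracheostomy' is a visit-form date that also counts intubation

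*SAP*

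**What the plan says.** **Population.** SAP 6.15.7 states: "Analysis will be performed on data combined for core study the Study VMALS-002-2 and for this extension study the Study VMALS-002-2b". SAP 6.15.6 (tracheostomy) likewise combines the two studies and lists the visits used. The visible text of neither section names an analysis set. SAP 6.4, 6.6, 6.8 and 6.14 each name theirs.

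The one set in SAP 6.1.1 is: "The safety analysis population will contain all Participants who sign the Informed Consent of the VMALS-002-2b study". Protocol 9.2 has: "The safety analysis population will contain all Participants who enroll in VMALS-002-2b". Protocol 5 sets the entry condition: "Participants who complete the Day 180 Visit in VMALS-002-2 are eligible to enroll in this extension study, VMALS-002-2b". Consent may come earlier. Protocol 5.1 lets people "provide written informed consent for this extension protocol (prior to, during, or after their Day 180 Visit in the VMALS-002-2 study", and Protocol 10.3.2 defines a participant as "Anyone who is consented for the Safety Evaluation during VMALS-002-2b on or prior to Day 180 of VMALS-002-2".

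**Time scale.** Under SAP 6.2.3, the mortality endpoint "will be calculated as the time period from date of first Study Drug Injection in the Study VMALS-002-2 to date of death", limited to 365 days and censored at the last visit. The example code in 6.15.6 has a time and a censoring flag but no entry time. SAP 3.2 gives the endpoint as "Time to all-cause mortality compared to Placebo".

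**Tracheostomy.** SAP 6.2.3 dates the event by the first ALSFRS-R form on which item 12 is scored 0, an answer that covers invasive ventilation by either intubation or tracheostomy.

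**The concern.** Two programmers could build different datasets from this text, and both would comply with it. One would take everyone injected in VMALS-002-2; the other would take the extension participants and their core-study data.

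On the second reading the clock and the set do not match. Apart from anyone who signed early, nobody in the set can die before Day 180. The curve is therefore flat to about that point by construction, yet it is presented as survival since first injection. The stated objective is whether Engensis benefits survival, so a reader would take it at face value.

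The tracheostomy curve has a separate fault. It would be labelled as one procedure, but it shows invasive ventilation by either route, dated at visits. A procedure followed by death before the next form is never counted. Neither is one followed by leaving the study without an early termination form; Protocol 7.1 asks for that assessment only where possible.

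**Working it through.** The documents give no event count or survival estimate for these endpoints, so there is no stated figure to reproduce. The results below are illustrations.

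**Inputs.** SAP 4 gives 18 as the maximum for the extension, based on core enrolment; I take 18 as the number injected. Two deaths among entrants after Day 180 are assumed. Core deaths, non-entrants and the allocation ratio are not given.

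**1. Overstatement of Day 365 survival.** Let d1 be deaths before Day 180, w people alive at Day 180 who do not enter (censored there), and d2 later deaths among entrants.

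- Extension set: 1 − d2/(18 − d1 − w)
- All injected: [(18 − d1)/18] × the same term
- Ratio: 18/(18 − d1) = 1/S(180), which is 1.000, 1.059 and 1.125 for d1 = 0, 1, 2

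With d2 = 2:

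| d1 | Extension set, w = 0 | All injected, w = 0 | Gap, w = 0 | Gap, w = 4 |
|---|---|---|---|---|
| 0 | 16/18 = 88.9% | 16/18 = 88.9% | 0 | 0 |
| 1 | 15/17 = 88.2% | 15/18 = 83.3% | 4.9 points | 4.7 points |
| 2 | 14/16 = 87.5% | 14/18 = 77.8% | 9.7 points | 9.3 points |

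**2. When 1/S(180) fails.**

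- *Early signers.* SAP 6.1.1 would count someone who signed and then died before Day 180. If the one early death had signed, both sets give 15/18 and the gap is 0. If one of two had, it is 14/17 = 82.4% against 77.8%, a gap of 4.6 points.
- *Non-entrants with different mortality.* Take d1 = 0 and w = 2, with x of those two dying by Day 365. The extension set gives 14/16 = 87.5% and the true value is (16 − x)/18 = 88.9%, 83.3% or 77.8%. The error is −1.4, +4.2 or +9.7 points.

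**3. Arm comparison**, with one later death per arm and one early death in one arm only:

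| Arms (assumed) | Arm with the early death | Difference, extension set | Difference, all injected | Shift |
|---|---|---|---|---|
| 9 v 9 | either | 7/8 v 8/9: 1.4 | 7/9 v 8/9: 11.1 | 9.7 points |
| 12 v 6 | the 12 | 10/11 v 5/6: 7.6 | 10/12 v 5/6: 0.0 | 7.6 points |
| 12 v 6 | the 6 | 11/12 v 4/5: 11.7 | 11/12 v 4/6: 25.0 | 13.3 points |

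With 9 v 9 and equal early deaths per arm the shift is 0.

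**4. How likely early deaths are.** Protocol 2.2.6.1 reports one death in 18 before 9 months. Under a constant hazard, the risk by Day 180 is 1 − (17/18)^(180/273.9) = 0.0369. Then 18 × 0.0369 = 0.66 deaths are expected, and P(none) = 0.51, P(one) = 0.35, P(two or more) = 0.14. The exact 95% interval for 1/18 (0.1% to 27.3%) gives 0.02 to 3.4 expected deaths. A constant hazard fitted to the same study's 36-month result (15 of 18 dead) gives 4.6, so the answer depends heavily on the input.

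**5. Does delayed entry alter the estimates?** With 17 entrants and four deaths after Day 180, Kaplan-Meier gives 0.941, 0.882, 0.824 and 0.765 with or without entry at Day 180, and the log-rank statistic is identical.

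**6. Form-date delay.** If events fall evenly between visits, mean delay = Σ(gap²/2)/Σgap.

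- Extension (gaps 60, 60, 65): 11,425/(2 × 185) = 30.9 days. The maximum with ±7-day windows and no missed visit is 65 + 7 + 7 = 79 days.
- Core study, from the visits in SAP 6.15.6 (gaps 30, 30, 24, 36, 24, 36): 5,544/(2 × 180) = 15.4 days.

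Dating precision therefore changes partway along a single curve.

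**The case against.** The strongest reply is that neither reading is a proven error. If all injected participants are meant, there is no truncation. If the extension set is meant, a reader can infer it because it is the only set defined, and the protocol says that this cohort completed Day 180. The list of tables is blacked out and may carry a population label. Step 5 shows that delayed entry changes no estimate after Day 180. The sizes rest on assumed deaths and arm sizes, no early death is the likeliest single count at the rate in step 4, and nothing in the documents suggests that early loss differs by arm. The item 12 rule is stated openly, applies the same schedule to both arms, and early termination visits include the ALSFRS-R.

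Most of this stands, and it limits the point to exploratory outputs and mainly to wording. It does not remove it. On the only defined set, following SAP 6.2.3 puts the origin of the mortality curve where the set has almost no one who could die. Disclosing the item 12 rule does not make intubation a tracheostomy, or a visit date a procedure date.

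**Conclusion.** The point holds and should be fixed. The visible SAP text leaves the population for both time-to-event analyses open. On the extension set, mortality is conditional on reaching Day 180 and consenting, but is shown as survival since first injection. The overstatement is 1/S(180) only if non-entrants alive at Day 180 have the same later mortality as entrants and no early signer dies before then. Under the stated assumptions that is 0 to 9.7 points for zero to two early deaths. With no early death and equal later mortality there is none. Bias in the arm comparison needs early death or non-entry to differ by arm; one such death shifts it by 7.6 to 13.3 points in the splits tried.

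The tracheostomy fault does not depend on which population is meant. Both endpoints are exploratory in at most 18 people, and the primary safety outputs are unaffected.

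**What to change.** - **Name the population in SAP 6.15.6 and 6.15.7.** Either:
  - (a) use everyone injected in VMALS-002-2, censor non-entrants at their last known event-free date, and note that this censoring may be informative; or
  - (b) keep the extension set, start mortality at Day 180 or use delayed entry, and label the curve as conditional on reaching Day 180 and consenting. This corrects the origin and the label; values after Day 180 stay the same.
- **In both cases, report by arm** how many died before Day 180 and how many did not enter the extension.
- **Relabel the item 12 endpoint** as time to invasive ventilation (intubation or tracheostomy). Report tracheostomy by recorded procedure date as a separate or sensitivity analysis, with one dating rule across both studies. The extension already collects procedure dates (Protocol 1.3, footnote 6, and 6.3). Use core dates only if VMALS-002-2 recorded them.
- **Minor:** censor mortality at the last date known alive, up to Day 365. This may add little, because Protocol 8.3.1 requires no active follow-up after participation ends.

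The cost is SAP wording, one label, minor code and a check of what VMALS-002-2 recorded. Option (a) goes beyond the population in Protocol 9.2, so SAP 9, which now declares no changes, would have to say so. Its added participants contribute follow-up only to about Day 180.

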7 INTERIM ANALYSIS

No interim analyses are planned.

8 DATA SAFETY MONITORING BOARD ANALYSIS

Data safety monitoring board (DSMB) analyses are described in a separate DSMB Statistical Analysis Plan.

9 CHANGES TO PLANNED PROTOCOL ANALYSIS

There are no changes to the planned protocol analysis.

QMD Ref: Worldwide-TMP-ST-005-7.0 Effective: 12Aug2019	Governing QMD: Worldwide-SOP-ST-001
Confidentiality Statement	

This document is the property of Worldwide Clinical Trials Inc. and may not be duplicated, copied, altered or removed from company without prior approval from Worldwide Quality Assurance or in compliance with Worldwide Standard Operating Procedures.

Worldwide Clinical Trials Controlled Quality Management Document			
 WORLDWIDE CLINICAL TRIALS	Sponsor:	Helixmith Co., Ltd.	
	Protocol Number:	VMALS-002-2b	
STATISTICAL ANALYSIS PLAN. PHASE 2-3-4			

